#### **6.9. Resistance Surveillance**

Sequence analysis of the HBV polymerase/reverse transcriptase (pol/RT) for resistance mutations may be attempted for all viremic subjects (HBV DNA  $\geq$  69 IU/mL). As it may not be known at the time of the visit whether a patient is viremic or if it will be their last study visit, a separate virology sample for potential resistance surveillance will be collected at each study visit.

#### **6.10. End of Study**

The end of this study will be the last subject's last observation (or visit).

## 7. ADVERSE EVENTS AND TOXICITY MANAGEMENT

### 7.1. Definitions of Adverse Events, Adverse Reactions, and Serious Adverse Events

#### 7.1.1. Adverse Events

An adverse event (AE) is any untoward medical occurrence in a clinical study subject administered a medicinal product, which does not necessarily have a causal relationship with the treatment. An AE can therefore be any unfavorable and/or unintended sign, symptom, or disease temporally associated with the use of a medicinal product, whether or not considered related to the medicinal product. AEs may also include pre- or post-treatment complications that occur as a result of protocol specified procedures, lack of efficacy, overdose, drug abuse/misuse reports, or occupational exposure. Preexisting events that increase in severity or change in nature during or as a consequence of participation in the clinical study will also be considered AEs.

An AE does not include the following:

- Medical or surgical procedures such as surgery, endoscopy, tooth extraction, and transfusion. The condition that led to the procedure may be an adverse event and must be reported.
- Pre-existing diseases, conditions, or laboratory abnormalities present or detected before the screening visit that do not worsen
- Situations where an untoward medical occurrence has not occurred (e.g., hospitalization for elective surgery, social and/or convenience admissions)
- Overdose without clinical sequelae (see Section 7.6.1)
- Any medical condition or clinically significant laboratory abnormality with an onset date before the consent form is signed and not related to a protocol-associated procedure is not an AE. It is considered to be pre-existing and should be documented on the medical history CRF.

#### 7.1.2. Serious Adverse Events

A **serious adverse event** (SAE) is defined as an event that, at any dose, results in the following:

- Death
- Life-threatening (Note: The term “life-threatening” in the definition of “serious” refers to an event in which the subject was at risk of death at the time of the event; it does not refer to an event that hypothetically might have caused death if it were more severe.)
- In-patient hospitalization or prolongation of existing hospitalization
- Persistent or significant disability/incapacity

- A congenital anomaly/birth defect
- A medically important event or reaction: such events may not be immediately life-threatening or result in death or hospitalization but may jeopardize the subject or may require intervention to prevent one of the other outcomes constituting SAEs. Medical and scientific judgment must be exercised to determine whether such an event is a reportable under expedited reporting rules. Examples of medically important events include intensive treatment in an emergency room or at home for allergic bronchospasm; blood dyscrasias or convulsions that do not result in hospitalization; and development of drug dependency or drug abuse. For the avoidance of doubt, infections resulting from contaminated medicinal product will be considered a medically important event and subject to expedited reporting requirements.

### **7.1.3. Clinical Laboratory Abnormalities and Other Abnormal Assessments as Adverse Events or Serious Adverse Events**

Laboratory abnormalities are usually not recorded as AEs or SAEs. However, laboratory abnormalities (e.g., clinical chemistry, hematology, urinalysis) independent of the underlying medical condition that require medical or surgical intervention or lead to investigational medicinal product interruption or discontinuation must be recorded as an AE, as well as an SAE, if applicable. In addition, laboratory or other abnormal assessments (e.g., electrocardiogram, X-rays, vital signs) that are associated with signs and/or symptoms must be recorded as an AE or SAE if they meet the definition of an AE (or SAE) as described in Sections 7.1.1 and 7.1.2. If the laboratory abnormality is part of a syndrome, record the syndrome or diagnosis (i.e., anemia) not the laboratory result (i.e., decreased hemoglobin).

Severity should be recorded and graded according to the GSI Grading Scale for Severity of Adverse Events and Laboratory Abnormalities ([Appendix 5](#)). For adverse events associated with laboratory abnormalities, the event should be graded on the basis of the clinical severity in the context of the underlying conditions; this may or may not be in agreement with the grading of the laboratory abnormality.

## **7.2. Assessment of Adverse Events and Serious Adverse Events**

The investigator or qualified sub investigator is responsible for assessing AEs and SAEs for causality and severity, and for final review and confirmation of accuracy of event information and assessments.

### **7.2.1. Assessment of Causality for Study Drugs and Procedures**

The investigator or qualified sub investigator is responsible for assessing the relationship to IMP therapy using clinical judgment and the following considerations:

- **No:** Evidence exists that the adverse event has an etiology other than the IMP. For SAEs, an alternative causality must be provided (e.g., pre-existing condition, underlying disease, intercurrent illness, or concomitant medication).
- **Yes:** There is reasonable possibility that the event may have been caused by the investigational medicinal product.

It should be emphasized that ineffective treatment should not be considered as causally related in the context of adverse event reporting.

The relationship to study procedures (e.g., invasive procedures such as venipuncture or biopsy) should be assessed using the following considerations:

- **No:** Evidence exists that the adverse event has an etiology other than the study procedure.
- **Yes:** The adverse event occurred as a result of protocol procedures, (e.g., venipuncture)

### **7.2.2. Assessment of Severity**

Severity of adverse events is to be determined based on GSI Grading Scale for Severity of Adverse Events and Laboratory Abnormalities ([Appendix 5](#)). A distinction should be drawn between seriousness and severity of AEs. An AE that is assessed as Grade 4 (potentially life-threatening) should not be confused with an SAE. Severity is a category utilized for rating the intensity of an event: both AEs and SAEs can be assessed as Grade 4. An event is defined as “serious” when it meets one of the predefined outcomes described above in Section [7.1.2](#).

### **7.3. Investigator Requirements and Instructions for Reporting Adverse Events and Serious Adverse Events to Gilead**

Requirements for collection prior to study drug initiation:

After informed consent, but prior to initiation of study medication, the following types of events should be reported on the case report form (CRF/eCRF): all SAEs and adverse events related to protocol-mandated procedures.

#### **Adverse Events**

Following initiation of study medication, collect all AEs, regardless of cause or relationship, until 30 days after last administration of study IMP. AEs must be reported to the CRF/eCRF database as instructed.

All AEs should be followed up until resolution or until the adverse event is stable, if possible. Gilead Sciences may request that certain AEs be followed beyond the protocol defined follow up period.

#### **Serious Adverse Events**

All SAEs, regardless of cause or relationship, that occurs after the subject first consents to participate in the study (i.e., signing the informed consent) and throughout the duration of the study, including the protocol–required post treatment follow-up period, must be reported to the CRF/eCRF database and Gilead Pharmacovigilance and Epidemiology (PVE), previously known as Drug Safety and Public Health, as instructed. This also includes any SAEs resulting from protocol-associated procedures performed after informed consent is signed.

Any SAEs and deaths that occur after the post treatment follow-up visit but within 30 days of the last dose of study IMP, regardless of causality, should also be reported.

Investigators are not obligated to actively seek SAEs after the protocol defined follow up 30 days period; however, if the investigator learns of any SAEs that occur after study participation has concluded and the event is deemed relevant to the use of IMP, he/she should promptly document and report the event to Gilead PVE.

- All AEs and SAEs will be recorded in the CRF/eCRF database within the timelines outlined in the CRF/eCRF completion guideline.

### Electronic Serious Adverse Event (eSAE) Reporting Process

- Site personnel record all SAE data in the eCRF database and from there transmit the SAE information to Gilead PVE within 24 hours of the investigator's knowledge of the event. Detailed instructions can be found in the eCRF completion guidelines.
- If for any reason it is not possible to record the SAE information electronically, i.e., the eCRF database is not functioning, record the SAE on the paper serious adverse event reporting form and submit within 24 hours to:

**Gilead PVE:** Fax: PPD [REDACTED]  
Email: PPD [REDACTED]

**Medical Monitor:** Name: PPD [REDACTED]  
Telephone: PPD [REDACTED]  
Fax: PPD [REDACTED]  
Email: PPD [REDACTED]

- As soon as it is possible to do so, any SAE reported via paper must be transcribed into the eCRF Database according to instructions in the eCRF completion guidelines.
- If an SAE has been reported via a paper form because the eCRF database has been locked, no further action is necessary.
- For fatal or life-threatening events, copies of hospital case reports, autopsy reports, and other documents are also to be submitted by e-mail or fax when requested and applicable. Transmission of such documents should occur without personal subject identification, maintaining the traceability of a document to the subject identifiers.
- Additional information may be requested to ensure the timely completion of accurate safety reports.
- Any medications necessary for treatment of the SAE must be recorded onto the concomitant medication section of the subject's CRF/eCRF and the event description section of the SAE form.

#### **7.4. Gilead Reporting Requirements**

Depending on relevant local legislation or regulations, including the applicable US FDA Code of Federal Regulations, the EU Clinical Trials Directive (2001/20/EC) and relevant updates, and other country-specific legislation or regulations, Gilead may be required to expedite to worldwide regulatory agencies reports of SAEs, serious adverse drug reactions (SADRs), or suspected unexpected serious adverse reactions (SUSARs). In accordance with the EU Clinical Trials Directive (2001/20/EC), Gilead or a specified designee will notify worldwide regulatory agencies and the relevant IEC in concerned Member States of applicable SUSARs as outlined in current regulations.

Assessment of expectedness for SAEs will be determined by Gilead using reference safety information specified in the investigator's brochure or relevant local label as applicable.

All investigators will receive a safety letter notifying them of relevant SUSAR reports associated with any study IMP. The investigator should notify the IRB or IEC of SUSAR reports as soon as is practical, where this is required by local regulatory agencies, and in accordance with the local institutional policy.

#### **7.5. Toxicity Management**

- All clinical and clinically significant laboratory toxicities will be managed according to uniform guidelines detailed in [Appendix 4](#).
- Grade 3 and 4 clinically significant laboratory abnormalities should be confirmed by repeat testing within 3 calendar days of receipt of results and before investigational medicinal product discontinuation, unless such a delay is not consistent with good medical practice.
- Clinical events and clinically significant laboratory abnormalities will be graded according to the Table for GSI Grading Scale for Severity of Adverse Events and Laboratory Abnormalities ([Appendix 5](#))
- When restarting investigational medicinal product following resolution of the adverse event, the investigational medicinal product should be restarted at full dose or modified dose that is dependent upon discussion with the Gilead Sciences Medical Monitor
- Any recurrence of the investigational medicinal product-related Grade 3 or 4 clinical or clinically significant laboratory adverse event following dose interruption mandates permanent discontinuation of investigational medicinal product
- Administration of study drug may be discontinued due to a clinical or laboratory event. The Gilead Medical Monitor should be consulted prior to dose discontinuation of study drug unless the investigator believes that immediate action is warranted to ensure the continued safety of subject
- Any questions regarding toxicity management should be directed to the Gilead Sciences Medical Monitor

### **7.5.1. Grades 1 and 2 Laboratory Abnormality or Clinical Event**

- Continue investigational medicinal product at the discretion of the investigator.

### **7.5.2. Grade 3 Laboratory Abnormality or Clinical Event**

- For Grade 3 clinically significant laboratory abnormality or clinical event, investigational medicinal product may be continued if the event is considered to be unrelated to investigational medicinal product.
- For a Grade 3 clinical event, or clinically significant laboratory abnormality confirmed by repeat testing, that is considered to be related to investigational medicinal product, investigational medicinal product should be withheld until the toxicity returns to  $\leq$  Grade 2.
- If a laboratory abnormality recurs to  $\geq$  Grade 3 following rechallenge with investigational medicinal product and is considered related to investigational medicinal product, then investigational medicinal product should be permanently discontinued and the subject managed according to local practice. Recurrence of laboratory abnormalities considered unrelated to investigational medicinal product may not require permanent discontinuation.

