### 7.5.5. Management of Potential Nephrotoxicity

eGFRCKD-EPI will be followed post-baseline during the study. All subjects on treatment with baseline eGFRCKD-EPI  $\geq 50$  mL/min/1.73m^2 that decline to  $< 50$  mL/min/1.73m^2 at any post-baseline visit and those with a post-baseline eGFRCKD-EPI  $< 30$  mL/min/1.73m^2 regardless of baseline eGFRCKD-EPI should have serum creatinine measured again within 3 calendar days of receipt of results. At the time of this repeat serum creatinine assessment, Cystatin C will also be measured and the estimated glomerular filtration rate (eGFR) by CKD-EPI (cystatin C) will be calculated and compared with the baseline measurement of this parameter.

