#### 7.5.5.1. For subjects on TDF:

- For subjects with baseline eGFRCKD-EPI  $\geq 50$  mL/min/1.73m^2 that decline to  $< 50$  mL/min/1.73m^2 at any post-baseline visit:
  - If the eGFRCKD-EPI is confirmed to be  $\geq 30$  mL/min/1.73m^2 and  $< 50$  mL/min/1.73m^2, the subject will be required to undergo dose modification to every other day dosing of TDF
  - If the eGFRCKD-EPI is confirmed to be  $\geq 30$  mL/min/1.73m^2 and  $< 50$  mL/min/1.73m^2, and the subject has undergone dose modification to every other day dosing of TDF and subsequently develops a confirmed eGFRCKD-EPI  $\geq 50$  mL/min/1.73m^2, the subject may revert to once daily dosing of TDF after discussion with the Gilead Medical Monitor
- For all subjects with a post-baseline eGFRCKD-EPI  $< 30$  mL/min/1.73 m^2 and  $\geq 15$  mL/min/1.73 m^2:
  - If the eGFRCKD-EPI is confirmed to be  $< 30$  mL/min/1.73m^2 and  $\geq 15$  mL/min/1.73 m^2, the subject will be required to undergo dose modification to every 96 hours dosing of TDF
  - If the eGFRCKD-EPI is confirmed to be  $< 30$  mL/min/1.73 m^2 and  $\geq 15$  mL/min/1.73 m^2, and the subject has undergone dose modification to once every 96 hours dosing of TDF and subsequently develops a confirmed CLCr  $\geq 30$  mL/min/1.73 m^2, the subject may revert to every other day dosing of study drug after discussion with the Gilead Medical Monitor
- For all subjects with a post-baseline eGFRCKD-EPI  $< 15$  mL/min/1.73 m^2:
  - If the eGFRCKD-EPI is confirmed to be  $< 15$  mL/min/1.73 m^2, the subject will be required to permanently discontinue treatment according to Section 7.5.5.3

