#### 7.5.5.2. For subjects on TAF:

- If the eGFRCKD-EPI is confirmed to be  $\geq 15$  mL/min/1.73 m^2, no dose modifications are required

7.5.5.3. For subjects on TAF or TDF:

- All subjects with a confirmed  $eGFR_{CKD-EPI} < 15 \text{ mL/min/1.73 m}^2$  will be required to permanently discontinue treatment
- All subjects with a change from baseline serum creatinine of  $\geq 0.4 \text{ mg/dL}$  must have serum creatinine repeated, with a concurrent urinalysis and urine chemistry, within two weeks of receipt of results

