Hypouricemia Adult and Pediatric ≥ 1 year	1.5 mg/dL to < LLN 87 μmol/L to < LLN	1.0 to < 1.5 mg/dL 57 to < 87 μmol/L	0.5 to < 1.0 mg/dL 27 to < 57 μmol/L	< 0.5 mg/dL < 27 μmol/L
Infant < 1 Year	N/A	1.0 mg/dl to < LLN- 57 μmol to < LLN	0.5 to < 1.0 mg/dL 27 to < 57 μmol/L	< 0.5 mg/dL < 27 μmol/L
Creatinine**	> 1.50 to 2.00 mg/dL > 133 to 177 μmol/L	> 2.00 to 3.00 mg/dL > 177 to 265 μmol/L	> 3.00 to 6.00 mg/dL > 265 to 530 μmol/L	> 6.00 mg/dL > 530 μmol/L

CHEMISTRY				
	Grade 1	Grade 2	Grade 3	Grade 4
Bicarbonate Adult and Pediatric ≥ 4 Years  Pediatric < 4 Years	16.0 mEq/L to < LLN 16.0 mmol/L to < LLN NA	11.0 to < 16.0 mEq/L 11.0 to < 16.0 mmol/L 11.0 mEq/L to < LLN 11.0 mmol/L to < LLN	8.0 to < 11.0 mEq/L 8.0 to < 11.0 mmol/L 8.0 to < 11.0 mEq/L 8.0 to < 11.0 mmol/L	< 8.0 mEq/L < 8.0 mmol/L < 8.0 mEq/L < 8.0 mmol/L
Triglycerides (Fasting)	NA	500 to 750 mg/dL 5.64–8.47 mmol/L	> 750 to 1200 mg/dL > 8.47–13.55 mmol/L	> 1200 mg/dL > 13.55 mmol/L
LDL (Fasting) Adult	130 to 160 mg/dL 3.35 to 4.15 mmol/L	>160 to 190 mg/dL >4.15 to 4.92 mmol/L	> 190 mg/dL >4.92 mmol/L	NA
LDL (Fasting) Pediatric >2 to <18 years	110 to 130 mg/dL 2.84 to 3.37 mmol/L	>130 to 190 mg/dL >3.37 to 4.92 mmol/L	> 190 mg/dL >4.92 mmol/L	NA
Hypercholesterolemia (Fasting)  Pediatric < 18 Years	200 to 239 mg/dL 5.16 to 6.19 mmol/L 170 to 199 mg/dL 4.39 to 5.15 mmol/L	> 239 to 300 mg/dL > 6.19 to 7.77 mmol/L > 199 to 300 mg/dL > 5.15 to 7.77 mmol/L	> 300 mg/dL > 7.77 mmol/L > 300 mg/dL > 7.77 mmol/L	NA  NA
Creatine Kinase	3.0 to < 6.0 × ULN	6.0 to < 10.0 × ULN	10.0 to < 20.0 × ULN	≥ 20.0 × ULN

\* Calcium should be corrected for albumin if albumin is < 4.0 g/dL

\*\* An overlap between the Grade 1 scale and the Lab's normal range for creatinine may result for Male subjects > 70 yrs. Please follow the Gilead convention of grading any result within the LLN and ULN a 0.

ENZYMES				
	Grade 1	Grade 2	Grade 3	Grade 4
AST (SGOT)	1.25 to 2.50 × ULN	> 2.50 to 5.00 × ULN	> 5.00 to 10.00 × ULN	> 10.00 × ULN
ALT (SGPT)	1.25 to 2.50 × ULN	> 2.50 to 5.00 × ULN	> 5.00 to 10.00 × ULN	> 10.00 × ULN
GGT	1.25 to 2.50 × ULN	> 2.50 to 5.00 × ULN	> 5.00 to 10.00 × ULN	> 10.00 × ULN
Alkaline Phosphatase	1.25 to 2.50 × ULN	> 2.50 to 5.00 × ULN	> 5.00 to 10.00 × ULN	> 10.00 × ULN
Total Amylase	> 1.0 to 1.5 × ULN	> 1.5 to 2.0 × ULN	> 2.0 to 5.0 × ULN	> 5.0 × ULN
Pancreatic Amylase	> 1.0 to 1.5 × ULN	> 1.5 to 2.0 × ULN	> 2.0 to 5.0 × ULN	> 5.0 × ULN

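### Creatinine above 3.00 mg/dL judged drug-related with eGFR still 15 or higher: Section 7.5.2 says to withhold study drug, Section 7.5.5.1 requires continued TDF every 96 hours, 7.5.5.2 requires no TAF change, and no readable text says which governs

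*Protocol*

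**What the plan says.** **General toxicity rules.** Protocol Section 7.5 places all clinically significant laboratory toxicities under the uniform guidelines of Appendix 4. Section 7.5.2 covers a clinically significant Grade 3 laboratory abnormality, confirmed on repeat, "that is considered to be related to investigational medicinal product, investigational medicinal product should be withheld until the toxicity returns to" Grade 2 or lower. Under Section 7.5, recurrence of a related Grade 3 or 4 event "following dose interruption mandates permanent discontinuation of investigational medicinal product"; Section 7.5.2 likewise ends treatment on related recurrence after rechallenge. The creatinine row of Appendix 5 puts Grade 3 at "> 3.00 to 6.00 mg/dL > 265 to 530 μmol/L", an absolute scale.

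**Renal rules.** Section 7.5.5 works from confirmed eGFR (CKD-EPI) and mentions neither toxicity grade nor causality.
- TDF, eGFR 15 to below 30 (7.5.5.1): "the subject will be required to undergo dose modification to every 96 hours dosing of TDF".
- TAF, eGFR 15 or above (7.5.5.2): "no dose modifications are required".
- Either drug, eGFR below 15 (7.5.5.3): subjects "will be required to permanently discontinue treatment".

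Sections 4.2 and 4.3 admit screening eGFR from 15 to below 90.

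**The concern.** A creatinine above 3.00 mg/dL can be Grade 3 while eGFR is still 15 or higher. If the investigator judges it clinically significant and related, one section says to stop dosing until the grade falls. For TDF the other requires dosing to continue on a longer interval. Neither section refers to the other.

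Two things are at stake. The first is patient safety. Section 1.3 says that re-infection of the graft is near universal without prophylaxis and that nucleos(t)ide treatment is lifelong, so whether drug is paused should not depend on which page is opened. The second is the data. SAP Section 7.1.7 tabulates adverse events leading to interruption, dose modification and discontinuation by arm. Under SAP Section 3.7.2, after premature discontinuation, laboratory values count as on-treatment only up to 3 days after the last dose. A permanent stop reached through the recurrence rule could therefore remove later eGFR and HBV DNA values from the on-treatment visits. Section 7.5.2 turns on an investigator's causality call in an open-label trial; Section 7.5.5 does not.

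**Working it through.** The documents give no figure to reproduce. The check asks whether Grade 3 creatinine and eGFR of 15 or higher can occur together, and over what range.

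**Inputs.** Grade 3 creatinine: above 3.00 up to 6.00 mg/dL (Appendix 5). Renal thresholds: 15 and 30 mL/min/1.73 m² (Section 7.5.5). Equation: SAP Section 7.4.3. Age, sex and race are assumptions; the table uses ages 50 to 70 without the race factor.

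**Formula.** With creatinine (SCr) above κ, the minimum term equals 1, so

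eGFR = 141 × (SCr/κ)^-1.209 × 0.993^age × (1.018 if female), with κ = 0.9 for men and 0.7 for women.

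Man aged 60 at 3.00 mg/dL: 141 × (3.00/0.9)^-1.209 × 0.993^60 = 141 × 0.2333 × 0.6561 = 21.6.

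Woman aged 60: 141 × 1.018 × (3.00/0.7)^-1.209 × 0.993^60 = 143.54 × 0.1721 × 0.6561 = 16.2.

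Solving for the creatinine at which eGFR is 15: SCr = κ × (141 × [1.018 if female] × 0.993^age / 15)^(1/1.209). For a man of 60 this is 0.9 × 6.167^0.827 = 4.05 mg/dL.

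| Sex, age | eGFR at 3.00 mg/dL | Creatinine at eGFR 15 (mg/dL) |
|---|---|---|
| Man, 50 | 23.1 | 4.30 |
| Man, 60 | 21.6 | 4.05 |
| Man, 70 | 20.1 | 3.82 |
| Woman, 50 | 17.4 | 3.39 |
| Woman, 60 | 16.2 | 3.20 |
| Woman, 70 | 15.1 | 3.02 |

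Both rules apply from just above 3.00 mg/dL up to the last column.

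**Sensitivity.** At 3.01 mg/dL, non-black men have eGFR of 15 or more at every age tested from 18 (28.9) to 80 (18.7). Non-black women do up to age 70. The race factor of 1.159 widens the range: at age 50, the highest creatinine with eGFR still at least 15 becomes 4.85 in men and 3.83 in women. Above 6.00 mg/dL eGFR is at most 14.5 for any adult, so the overlap is confined to Grade 3. Nearly all of it lies below 30, in the 96-hour TDF band. The exception is black men up to age 33 with creatinine just above 3.00.

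**The rules side by side** for a man of 60 at a confirmed 3.5 mg/dL (eGFR 17.9), judged clinically significant and related:
- Section 7.5.2: withhold until Grade 2 or lower, that is 3.00 mg/dL or below.
- Section 7.5.5.1, if on TDF: dosing every 96 hours is required.
- Section 7.5.5.2, if on TAF: no modification is required.
- Section 7.5.5.3: the stopping threshold of 15 is not reached.

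**The case against.** **The specific section overrides the general one.** There is a parallel in the protocol. ALT above 10 × ULN is Grade 4, for which Section 7.5.3 ends treatment if the result is confirmed, clinically significant and related, yet Section 7.5.6.1 lets some such subjects stay on drug. Section 7.5.5 could be read in the same way. That reading is reasonable, but it is not written down. Section 7.5 covers all clinically significant laboratory toxicities, Section 7.5.3 spells out its own exceptions, and Section 6.6 lists unacceptable toxicity and eGFR below 15 as separate grounds for discontinuation. The Appendix 4 chart could not be read and might settle the matter.

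**The TAF arm has no contradiction.** Largely right. A reader might infer opposite orders in both arms, but Section 7.5.5.2 only says that changes are not required. Withholding TAF under Section 7.5.2 breaches nothing in it.

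**IMP may not include TDF.** Section 5 describes only TAF. However, Section 7.5.5.1 calls TDF study drug in its clause on reverting to more frequent dosing, and Section 8.6 summarizes by IMP received across treatment groups. The direct conflict rests on that reading.

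**Stronger inferences that the documents do not support.**
- *Conflicting repeat-test windows.* The two-week repeat in Section 7.5.5.3 might seem to clash with the 3 days in Section 7.5. But for any post-baseline eGFR below 30, Section 7.5.5 already says that subjects "should have serum creatinine measured again within 3 calendar days of receipt of results". A repeat within 3 days, with the urine tests, satisfies every clause.
- *Subjects enrolled at Grade 3 must be withheld at once.* Grade alone does not trigger Section 7.5.2; clinical significance and relatedness are also needed. Section 7.1.1 does not count an unchanged pre-existing abnormality as an adverse event.
- *The overlap makes the arms non-comparable.* Section 7.5.5 already adjusts TDF and not TAF by design, and the primary safety endpoint is change in eGFR, not dose changes.
- *Sites will diverge, and subjects will lose antiviral cover.* About one center is planned, the Medical Monitor takes toxicity questions, and Arm B may include other antivirals.

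**Conclusion.** The inconsistency is real but narrow. For a confirmed, clinically significant, related creatinine above 3.00 mg/dL with eGFR of 15 or higher, the TDF arm has two instructions that cannot both be followed on the same day, and the TAF arm has an unclear one. The overlap is eGFR 15 to about 20-23 in men aged 50 to 70. In women it is 15 to about 17 at age 50 and almost nothing at age 70.

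This rests on the SAP equation without the race factor, on IMP including TDF, and on Appendix 4 containing no precedence rule. The documents do not allow a count of affected subjects; with about 50 planned it may be few. The point deserves correction because it concerns when antiviral treatment is paused in transplant recipients, in a trial whose primary safety question is renal. It does not show that the primary comparison is biased.

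**What to change.** Reconcile Sections 7.5 (including the recurrence rule), 7.5.2, 7.5.5 and Appendix 4. State in Section 7.5 which section governs creatinine and eGFR findings in each arm, and whether IMP in the toxicity rules includes TDF. The sponsor's clinical team must choose the governing rule; none is proposed here.

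The cost is a wording change or a clarification letter, with no new visits, tests or subjects. SAP Sections 2.1.2 and 2.1.3 report the Week 24 and Week 48 analyses as done, so for the randomized phase the practical step is for the study report to state, by arm, which rule was applied to any subject who met both.
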